#### 4. Ethnicity

- Hispanic or Latino
- Not Hispanic or Latino

#### 5. Religion

- Catholic
- Protestant
- Jewish
- Muslim
- None
- Other (please specify) \_\_\_\_\_

#### 6. Please indicate your highest or current education level

- 11th grade or less
- High school graduate or GED
- 2 years of college/AA degree/Technical school training
- College graduate (BA or BS)
- Masters degree
- Doctorate/Medical degree/Law degree

#### 7. Relationship status

- Married or living with someone as if married
- Non-cohabiting relationship
- Single, never married
- Divorced or separated
- Loss of long-term partner/widowed
- Other (please specify) \_\_\_\_\_

#### 8. Please indicate who (if anyone) you live with (you may check more than one box)

- Self only
- Partner/Spouse
- Roommate/Friend
- Dependent Children  
If yes, specify number(s) \_\_\_\_\_
- If yes, specify age(s) \_\_\_\_\_
- Group home/Residential
- Independent Child
- Dependent Adult
- Parent
- Other (please specify) \_\_\_\_\_

#### 9. Employment Status: (you may check more than one box)

- Full time work
- Part time work
- Retired
- Paid leave
- Unpaid leave
- Other (please specify) \_\_\_\_\_

#### 10. What is your annual combined household income?

- Less than \$25,000
- \$25,000 – 50,000
- \$51,000 -100,000
- \$101,000 – 150,000
- Greater than \$150,000

#### 11. Please indicate how long you have known

the patient: \_\_\_\_\_ years

#### 12. Do you live in the same residence as the patient?

- Yes
- No

### **31.04 Locator Form**

#### **Locator Form**

Please complete the following legibly.

Full name: \_\_\_\_\_

Address: \_\_\_\_\_  
\_\_\_\_\_

Cell phone: \_\_\_\_\_

Home phone: \_\_\_\_\_

Work phone: \_\_\_\_\_

Email address: \_\_\_\_\_

What is your preferred contact method for scheduling? (circle one): **phone call / text message / e-mail**

Date of birth (month/day/year): \_\_\_\_\_ / \_\_\_\_\_ / \_\_\_\_\_

## 31.05 Caregiver Oncology Quality of Life

### Concerning the person you help, have you:

1. Been worried, anxious?

- Never/ Not at all
- Rarely / a little bit
- Sometimes / Somewhat
- Often / A lot
- Always / Very Much

2. Been sad, depressed?

- Never/ Not at all
- Rarely / a little bit
- Sometimes / Somewhat
- Often / A lot
- Always / Very Much

3. Felt emotionally tired, worn out?

- Never/ Not at all
- Rarely / a little bit
- Sometimes / Somewhat
- Often / A lot
- Always / Very Much

4. Been stressed?

- Never/ Not at all
- Rarely / a little bit
- Sometimes / Somewhat
- Often / A lot
- Always / Very Much

5. Felt a lack of freedom?

- Never/ Not at all
- Rarely / a little bit
- Sometimes / Somewhat
- Often / A lot
- Always / Very Much

6. Been bothered by the feeling of being confined?

- Never/ Not at all
- Rarely / a little bit
- Sometimes / Somewhat
- Often / A lot
- Always / Very Much

7. Been bothered by the fact that your life was entirely devoted to the care recipient?

- Never/ Not at all
- Rarely / a little bit
- Sometimes / Somewhat
- Often / A lot
- Always / Very Much

8. Been embarrassed to be the only person to provide assistance?

- Never/ Not at all
- Rarely / a little bit
- Sometimes / Somewhat
- Often / A lot
- Always / Very Much

9. Been satisfied with information given by health care providers (doctors, nurses...)?

- Never/ Not at all
- Rarely / a little bit
- Sometimes / Somewhat
- Often / A lot
- Always / Very Much

10. Been reassured by the health care providers (doctors, nurses...)?

- Never/ Not at all
- Rarely / a little bit
- Sometimes / Somewhat
- Often / A lot
- Always / Very Much

11. Felt that your role as caregiver was recognized by health care providers (doctors, nurses...)?

- Never/ Not at all
- Rarely / a little bit
- Sometimes / Somewhat
- Often / A lot
- Always / Very Much

12. Had financial difficulties?

- Never/ Not at all
- Rarely / a little bit
- Sometimes / Somewhat
- Often / A lot
- Always / Very Much

13. Had other difficulties (lodging, transportation...)?

- Never/ Not at all
- Rarely / a little bit
- Sometimes / Somewhat
- Often / A lot
- Always / Very Much

14. Encountered difficulties in the administrative process (health insurance paperwork and other paperwork related to the cancer illness)?

- Never/ Not at all
- Rarely / a little bit
- Sometimes / Somewhat
- Often / A lot
- Always / Very Much

15. Experienced feelings of guilt?

- Never/ Not at all
- Rarely / a little bit
- Sometimes / Somewhat
- Often / A lot
- Always / Very Much

16. Been bothered by a feeling of helplessness against the disease?

- Never/ Not at all
- Rarely / a little bit
- Sometimes / Somewhat
- Often / A lot
- Always / Very Much

17. Felt a feeling of injustice, anger, or rebellion?

- Never/ Not at all
- Rarely / a little bit
- Sometimes / Somewhat
- Often / A lot
- Always / Very Much

18. Had sleeping difficulties?

- Never/ Not at all
- Rarely / a little bit
- Sometimes / Somewhat
- Often/ A lot
- Always / Very Much

19. Had problems with your appetite?

- Never/ Not at all
- Rarely / a little bit
- Sometimes / Somewhat
- Often / A lot
- Always / Very Much

20. Been physically tired, worn out?

- Never/ Not at all
- Rarely / a little bit
- Sometimes / Somewhat
- Often / A lot
- Always / Very Much

21. Had the impression that your health was fragile?

- Never/ Not at all
- Rarely / a little bit
- Sometimes / Somewhat
- Often / A lot
- Always / Very Much

22. Felt you made a difference for the person you are helping?

- Never/ Not at all
- Rarely / a little bit
- Sometimes / Somewhat
- Often / A lot
- Always / Very Much

23. Felt useful?

- Never/ Not at all
- Rarely / a little bit
- Sometimes / Somewhat
- Often / A lot
- Always / Very Much

24. Could rest, relax??

- Never/ Not at all
- Rarely / a little bit
- Sometimes / Somewhat
- Often / A lot
- Always / Very Much

25. Could take care of yourself, pay attention to your own health?

- Never/ Not at all
- Rarely / a little bit
- Sometimes / Somewhat
- Often / A lot
- Always / Very Much

26. Been assisted, supported, understood by your family?

- Never/ Not at all
- Rarely / a little bit
- Sometimes / Somewhat
- Often / A lot
- Always / Very Much

27. Been assisted, supported, understood by your friends?

- Never/ Not at all
- Rarely / a little bit
- Sometimes / Somewhat
- Often / A lot
- Always / Very Much

28. Had difficulties in your intimate, emotional life?

- Never/ Not at all
- Rarely / a little bit
- Sometimes / Somewhat
- Often / A lot
- Always / Very Much

29. Had a satisfying love and sexual life?

- Never/ Not at all
- Rarely / a little bit
- Sometimes / Somewhat
- Often / A lot
- Always / Very Mu

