#### 9.5.5 Caregiver Quality of Life (QoL)

We will use the CareGiver Oncology QoL questionnaire (CarGOQoL), a 29-item, well-validated instrument specific to caregivers for patients with cancer, to measure family caregiver QoL in multiple domains. It is estimated that the CarGOQoL ([Appendix 31.05](#)) will take approximately 2-4 minutes to complete.

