## 11.2 Analysis Plan

Feasibility will be defined by rates of enrollment and participation. We will report the proportion of eligible caregivers who agree to participate in the intervention and the proportion of intervention visits completed by each participant. Additionally, we will examine reasons for declining participation, incomplete session attendance, and early withdrawal from the study. The intervention will be deemed feasible if at least 70% (+/- 18%) of eligible caregivers are enrolled in the study and if at least 70% of enrolled participants complete  $\geq 50\%$  of the sessions. We will use descriptive statistics to summarize the demographic and clinical characteristics of caregivers enrolled in the study. We will audio-record and transcribe the individual semi-structured exit interviews and analyze qualitative data according to NIH Best Practices for Mixed Methods Research in the Health Sciences. Study staff will independently review the transcripts to create a thematic framework for interpretation. Two individuals, including the Principal Investigator, will independently code the data to enhance validity and credibility, until high reliability is achieved (Kappa>0.80). The planned sample size will allow us to collect comprehensive feedback and ensures sufficient number of participants to achieve thematic saturation. In an exploratory analysis, we will also examine changes in caregiver-reported outcomes from baseline to post-intervention using paired t-tests.

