## 31.02 Hospital Anxiety and Depression Scale (HADS)

**INSTRUCTIONS:** Read each item and please select the answer which comes closest to how you have been feeling, on the average, IN THE PAST WEEK:

1. I feel tense or "wound up."
  - a. Most of the time
  - b. A lot of the time
  - c. From time to time, occasionally
  - d. Not at all
2. I still enjoy the things I used to enjoy.
  - a. Definitely as much
  - b. Not quite as much
  - c. Only a little
  - d. Hardly at all
3. I get a sort of frightened feeling as if something awful is about to happen.
  - a. Very definitely and quite badly
  - b. Yes, but not too badly
  - c. A little, but it doesn't worry me
  - d. Not at all
4. I can laugh and see the funny side of things.
  - a. As much as I always could
  - b. Not quite so much now
  - c. Definitely not so much now
  - d. Not at all
5. Worrying thoughts go through my mind.
  - a. A great deal of the time
  - b. A lot of the time
  - c. From time to time but not too often
  - d. Only occasionally
6. I feel cheerful.
  - a. Not at all
  - b. Not often
  - c. Sometimes
  - d. Most of the time
7. I can sit at ease and feel relaxed.
  - a. Definitely
  - b. Usually
  - c. Not often
  - d. Not at all
8. I feel as if I am slowed down.
  - a. Nearly all the time
  - b. Very often
  - c. Sometimes
  - d. Not at all

9. I get a sort of frightened feeling like "butterflies" in the stomach.

- a. Not at all
- b. Occasionally
- c. Quite often
- d. Very often

11. I feel restless as if I have to be on the move.

- a. Very much indeed
- b. Quite a lot
- c. Not very much
- d. Not at all

13. I get sudden feelings of panic.

- a. Very often indeed
- b. Quite often
- c. Not very often
- d. Not at all

10. I have lost interest in my appearance.

- a. Definitely
- b. I don't take so much care as I should
- c. I may not take quite as much care
- d. I take just as much care as ever

12. I look forward with enjoyment to things.

- a. As much as I ever did
- b. Rather less than I used to
- c. Definitely less than I used to
- d. Hardly at all

14. I can enjoy a good book or radio or TV

program.

- a. Often
- b. Sometimes
- c. Not often
- d. Very seldom

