### 31.06 Caregiver Reaction Assessment

Please answer the following items with regards to caring for your loved one during their illness.

	Strongly agree	Agree	Neither agree or disagree	Disagree	Strongly disagree
I feel privileged to care for my loved one					
Others have dumped caring for my loved one onto me					
My financial resources are adequate to pay for things that are required for caregiving					
My activities are centered around care for my loved one					
Since caring for my loved one, it seems like I am tired all the time					
It is very difficult to get help from my family in taking care of my loved one					
I resent having to take care of my loved one					
I have to stop in the middle of work					
I really want to care for my loved one					
My health has gotten worse since I have been caring for my loved one					
I visit family and friends less since I have been caring for my loved one					
I will never be able to do enough caregiving to repay my loved one					
My family works together at caring for my loved one					
I have eliminated things from my schedule since caring for my loved one					
I have enough physical strength to care for my loved one					
Since caring for my loved one, I feel my family has abandoned me					
Caring for my loved one makes me feel good					
The constant interruptions make it difficult to find time for relaxation					
I am healthy enough to care for my loved one					
Caring for my loved one is important to me					
Caring for my loved one has put a financial strain on the family					
My family (brothers, sisters, children) left me alone to care for my loved one					
I enjoy caring for my loved one					

It is difficult to pay for my loved one's health needs and services					
---	--	--	--	--	--

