### **31.07 Lewis Cancer Self-Efficacy Scale**

**CASE: Cancer Self-efficacy Scale**

Patient Version

Instructions:

We would like to know how confident or sure you feel about some of these areas that arise when you are going through **the experience of caring for a loved one with cancer**. Please rate your degree of confidence for each sentence by circling a number from 0 to 10 using the scale shown. When you choose a higher number, you are telling us you are more confident.

Rate the confidence you feel TODAY	Not at all confident	Very confident									
1. I am confident that I can use information and resources to cope with the demands of my loved one's illness.	0	1	2	3	4	5	6	7	8	9	10
2. I am confident that I can call on my inner strengths to pull myself through my loved one's illness.	0	1	2	3	4	5	6	7	8	9	10
3. I am confident that I have what it takes to help my family through my loved one's illness.	0	1	2	3	4	5	6	7	8	9	10
4. I am confident that I can maintain close communication with my loved one about their illness.	0	1	2	3	4	5	6	7	8	9	10
5. I am confident that I can take the necessary steps to work through the demands of my loved one's illness.	0	1	2	3	4	5	6	7	8	9	10
6. I am confident that I have what it takes to help my family handle this illness.	0	1	2	3	4	5	6	7	8	9	10
7. I am confident that I can handle the challenges of my loved one's illness.	0	1	2	3	4	5	6	7	8	9	10
8. I am confident that I have ways to manage the uncertainty brought on by my loved one's illness.	0	1	2	3	4	5	6	7	8	9	10
9. I am confident that I can manage difficult interactions with my loved one's doctors, nurses, and other health care providers.	0	1	2	3	4	5	6	7	8	9	10
10. I am confident that I can put my loved one's illness into proper perspective in my life.	0	1	2	3	4	5	6	7	8	9	10

Rate the confidence you feel TODAY

Not at all

Very

	confident										confident
11. I am confident that I have the ability emotionally to help my family work through the issues caused by my loved one's illness.	0	1	2	3	4	5	6	7	8	9	10
12. I am confident that I can deal with the physical changes caused by my loved one's illness.	0	1	2	3	4	5	6	7	8	9	10
13. I am confident that I can manage what is being asked of me despite this illness.	0	1	2	3	4	5	6	7	8	9	10
14. I am confident that I have the skills to deal with the pressures the illness is causing in my close relationships.	0	1	2	3	4	5	6	7	8	9	10

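### The CarGOQoL as printed has no recall period, so its post-intervention answers may reach back before session 1 and the exploratory quality-of-life change may be attenuated

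*Combined protocol and SAP*

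**What the plan says.** The data table in section 11.3 lists five instruments given both pre- and post-intervention: HADS, CarGOQoL, CRA, CASE and MOCS. Section 11.2 says of them: "we will also examine changes in caregiver-reported outcomes from baseline to post-intervention using paired t-tests". Section 11.1 adds that the pilot data are meant to supply an effect size for a later multi-center randomized trial.

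Section 9.5.5 describes the CarGOQoL as "a 29-item, well-validated instrument specific to caregivers for patients with cancer" and gives no recall period. Appendix 31.05 prints the form. It begins with the item stem "Concerning the person you help, have you", lists 29 items, and offers five answers from Never/Not at all to Always/Very Much. No time frame appears anywhere on it.

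The neighbouring forms do print one:

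- HADS (31.02): "how you have been feeling, on the average, IN THE PAST WEEK".
- CASE (31.07): "Rate the confidence you feel TODAY".
- MOCS (31.08): what the caregiver can currently do.
- GAD-7 (31.01, screening only): the last two weeks.

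The CRA (31.06) has an instruction of a different kind: "Please answer the following items with regards to caring for your loved one during their illness".

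**The concern.** A frequency answer needs a period to refer to. Without one, a caregiver asked at the end of the program how often they had sleeping or financial difficulties may count episodes from before session 1. The period covered by the second questionnaire then contains the period covered by the first, and part of any real improvement is averaged away.

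The pre-program period can be longer than the program. Section 3.0 admits caregivers up to 6 months after the patient's diagnosis, and section 7.0 puts participation at about 6 to 12 weeks. Both vary between caregivers, so any attenuation would vary too.

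At stake are the exploratory quality-of-life change and its use in planning a later trial. A small CarGOQoL change could mean that the program does little for quality of life, or only that the form looked back too far. Once the data are collected, the two cannot be told apart.

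**Working it through.** **Plan's own figure.** The plan states no effect size, standard deviation, significance level or power for the paired changes, so there is nothing to reproduce on this point.

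**Wording check.** Of the five pre/post forms, HADS, CASE and MOCS are tied to the past week, today and the present. The CarGOQoL has no time reference. The CRA is framed by the illness, and its 24 items are mixed:

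- 5 use the word *since* for the time caring began, for example "My health has gotten worse since I have been caring for my loved one".
- 3 more describe events to date (having had care dumped on them, financial strain, being left alone).
- About 16 are plain present-tense statements, for example "I have enough physical strength to care for my loved one".

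**Illustrative worst case for the CarGOQoL.** Assume, as the documents do not, that:

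- each answer is an equal-weight average over all the time since diagnosis;
- the true level is constant before the program;
- it shifts by an amount D at program start and stays there.

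Let t0 be the months from diagnosis to entry and L the program length. The baseline answer then reflects the old level only. The post answer has weight L/(t0 + L) on the new level. So:

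observed change = D × L/(t0 + L)

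L is 6 weeks (1.38 months) or 12 weeks (2.76 months), from section 7.0. Values of t0 are chosen within the 6-month limit of section 3.0.

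| Entry (t0) | 6-week program | 12-week program |
|---|---|---|
| Month 1 | 1.38/2.38 = 58% | 2.76/3.76 = 73% |
| Month 3 | 1.38/4.38 = 32% | 2.76/5.76 = 48% |
| Month 6 | 1.38/7.38 = 19% | 2.76/8.76 = 32% |

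**Around that case:**

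- If every caregiver answers about the present, 100% is retained.
- If half do so and half average (month 3, 6 weeks), 0.5 × 1 + 0.5 × 0.32 = 66% is retained.
- If improvement is linear over the program rather than a step, the averaged level within the program is half the final gain, so each share in the table halves.

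**What it could mean for the t-test.** Assume a standardized change of 0.6, two-sided 5%, all 25 caregivers with paired data, and an unchanged standard deviation of change. Power by the noncentral t is 82% with no attenuation. It is 56% at 73% retained, 28% at 48%, and 8% at 19%. These figures show sensitivity only; the 0.6 is not from the plan.

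**The case against.** **Attenuation is possible, not shown.** A reader might infer from the wording that the paired changes are in fact biased toward zero. The documents do not support that. Caregivers may answer about how things are now, and five graded answers, which pair frequency with intensity words, can move when a difficulty eases. This stands, and it is why the range must include no loss at all.

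**The form as given may differ from the appendix.** HADS, CRA, CASE and MOCS each print an instruction to the respondent, while the CarGOQoL starts straight at its stem. An instruction may exist and not be reproduced. This also stands. It makes the first step a confirmation, but section 9.5.5 does not settle the matter either.

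**The CRA.** A stronger reading would treat the CRA as having the same defect. The documents do not bear this out. Its reference to the illness can simply describe the caring, which is still going on at both visits, and about 16 of 24 items are present-tense agreement statements that a time-averaging model does not describe. If only the 5 to 8 cumulative items were diluted, at 19% to 75% retained each, a total score would keep about 73% to 95% of its change: 1 − (8/24)(0.81) = 73% and 1 − (5/24)(0.25) = 95%. Adding a past-week instruction would also contradict the five *since* items.

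**Limited reach.** The primary endpoint is feasibility, and anxiety and coping, the program's stated targets, are measured by HADS and MOCS. A reader might also object that the CarGOQoL change could not be compared with changes on the other scales, but no such comparison is planned. This limits the weight of the point. It does not remove it, because section 11.1 gives the pilot data a planning use.

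**Conclusion.** The point holds for the CarGOQoL, as a possibility of unknown size. What is firm is the wording: a Never-to-Always scale with no recall period, analysed as paired change, for caregivers who may enter months after diagnosis. What is not firm is the effect. It runs from none, if caregivers answer about the present, down to 19% to 73% of a step change retained under full averaging since diagnosis with entry at month 1 to 6. That lower range is an illustrative worst case within a step-change model, not an estimate.

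For the CRA, only a caveat is justified: its five *since* items and its illness-wide frame may make its change scores less responsive.

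The feasibility endpoint and the HADS, CASE and MOCS changes are unaffected. The change is worth making because it costs almost nothing and cannot be made after data collection.

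**What to change.** 1. Confirm whether the CarGOQoL as administered carries a recall instruction that Appendix 31.05 does not show.
2. Print one identical recall period on the CarGOQoL at both visits, in the appendix and in any electronic version. Use the instrument's own period if it has one and it fits; otherwise choose one. It should be no longer than the 6-week minimum program length, so that the post-intervention window does not reach back before the program. A window well inside six weeks is better, since a window as long as the program still averages over its early weeks.
3. State the period in section 9.5.5 or 11.2.
4. Leave the CRA wording unchanged. Add a sentence to section 11.2 that its *since* items and illness-wide frame may make its change less responsive.

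The cost is one instruction line and two sentences of protocol text, with no added burden for caregivers. The small downside is slightly reduced comparability of CarGOQoL scores with studies that used another instruction. Items such as insurance paperwork or finances may suit a very short window poorly, which should be weighed when the period is chosen.

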### 31.06 Caregiver Reaction Assessment

Please answer the following items with regards to caring for your loved one during their illness.

	Strongly agree	Agree	Neither agree or disagree	Disagree	Strongly disagree
I feel privileged to care for my loved one					
Others have dumped caring for my loved one onto me					
My financial resources are adequate to pay for things that are required for caregiving					
My activities are centered around care for my loved one					
Since caring for my loved one, it seems like I am tired all the time					
It is very difficult to get help from my family in taking care of my loved one					
I resent having to take care of my loved one					
I have to stop in the middle of work					
I really want to care for my loved one					
My health has gotten worse since I have been caring for my loved one					
I visit family and friends less since I have been caring for my loved one					
I will never be able to do enough caregiving to repay my loved one					
My family works together at caring for my loved one					
I have eliminated things from my schedule since caring for my loved one					
I have enough physical strength to care for my loved one					
Since caring for my loved one, I feel my family has abandoned me					
Caring for my loved one makes me feel good					
The constant interruptions make it difficult to find time for relaxation					
I am healthy enough to care for my loved one					
Caring for my loved one is important to me					
Caring for my loved one has put a financial strain on the family					
My family (brothers, sisters, children) left me alone to care for my loved one					
I enjoy caring for my loved one					

It is difficult to pay for my loved one's health needs and services					
---	--	--	--	--	--

